8.2 Study Assessments

8.2.1 Distress/Mood Assessments

- Kessler Psychological Distress Scale (K10)¹²¹: 10-item questionnaire intended to yield a global measure of distress based on questions about anxiety and depressive symptoms that a person has experienced in the past 4 week period.
- Positive and Negative Affect (PANAS)¹²²: 20-item self-report questionnaire that measures positive and negative affect.
- Beck Depression Inventory (BDI)¹²³: it is a self-report instrument intended to assess the existence and severity of symptoms of depression.
- State-Trait Anxiety Inventory (STAI)¹²⁴: it is a psychological inventory based on a 4-point Likert scale and consists of 40 questions on a self-report basis to assess anxiety and trait anxiety.

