4.2 Study Endpoints

4.2.1 Primary Study Endpoints

- Change in distress measured by Kessler Psychological Distress Scale (K10) and Positive and Negative Affect Schedule (PANAS) between baseline and treatment-end.
- Change in cannabis use measured by Timeline Followback Method Assessment (TLFB), Marijuana Craving Questionnaire (MCQ-17), Daily Sessions, Frequency, Age of Onset, and Quantity of Cannabis-Use Inventory (DFAQ-CU) and Cannabis Withdrawal Scale (CWS) between baseline and treatment-end.

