6.1.4 Dosing and Administration

The tDCS device will deliver each session 2.0 mA for 20 minutes over the DLPFC. Participants will receive 20 intervention sessions over the course of this study on weekdays (M-F).

Study technicians are always live with participants via Zoom or Webex when initiating and delivering the treatment and can address any issues that arise during treatment. Study technicians will direct headset placement remotely. The tDCS device can only operate if: **1)** the headset is correctly placed for adequate connection, and **2)** the study technician provides a session code that unlocks the device for a one-time only 20-minute period of use.

If the device loses adequate electrode contact for any reason, the device will automatically discontinue the session. The session can only be reestablished if another unlock code is provided by the study technician. Specific stop criteria are outlined for treatment administration. Should any stop criteria be met at any point in administration of treatment, the participant will not undergo any further treatments and will be asked to return the study equipment (See Fig 3). If the participant wishes to discontinue a session, they may press the "abort" key at any time, which ramps down and stops the stimulation current within 30 seconds.

CONFIDENTIAL

This material is the property of the NYU School of Medicine and Langone Medical Center. Do not disclose or use except as authorized in writing by the study sponsor
Interventional Template Version: 11 January 2019

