6.1.6 Duration of Intervention

Participants will complete 20 sessions of either active or sham RS-tDCS over the course of approximately 4-6 weeks. The tDCS will be programmed to deliver 20 minutes of stimulation.

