While the remote connection does allow for a participant to provide a sample that is not their own to test, we believe that this occurrence would be of very low likelihood in this study sample. The participants are enrolled based on disclosed cannabis use, they are not incentivized in any way to decrease their cannabis use, and there would be no other primary or secondary gain for invalidating this procedure. Alternatively, in the similarly unlikely event that participants have falsely reported cannabis use and test negative at baseline, they will be withdrawn.

- Participants will complete self-report questionnaires about their physical and mental health, and cannabis use through REDCap survey function (see assessments section 8.2 below).
- For exploratory research, participants will complete cognitive measures (BICAMS, Cogstate Brief Battery) and MS symptom questionnaires.
- Participants will have their first 20-minute tDCS session of either 2.0mA active or sham tDCS combined with mindfulness meditation. At each treatment session, participants will complete brief adverse event reports before and after each session. Once the study technician visually confirms correct headset placement and participants confirms adequate contact quality (moderate or good), the technician will provide the participant with a one-time use unlock code to enter into their tDCS device. The participant enters the code when ready to initiate the stimulation. During each stimulation session participants will listen to a guided mindfulness meditation audio track on the study provided laptop computer.
- Remotely-Supervised tDCS Sessions 2-20:
 - Over the next 4-6 weeks, participants will complete the remaining daily tDCS + mindfulness meditations as described above for session 1.
 - After sessions 5, 10, and 15 participants will complete self-report questionnaires using REDCap survey function.
 - tDCS session 20 & Treatment-end: After completing the final tDCS session participants will repeat the baseline self-report questionnaires and measures, and the single panel cannabis test. Participants will be asked to return the equipment via Fedex using a prepaid return label.
- Post treatment-end follow-ups

CONFIDENTIAL

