10.4.2 Analysis of the Primary and Secondary Endpoint(s)

The efficacy of RS-tDCS to effect the outcomes of each Aim 1 & 2 will be tested using linear mixed effects models. The dependent measures (K10 score, NA, percent of days of use, CWS, MCQ-17) will be nested within timepoint (Visit 1, 5, 10, 15, 20), with active/sham as fixed effects. This will be done using the Matlab function 'fitlme' with REML estimation predicting change from V1 values following each 5 session RS-tDCS interval (Matlab, R2020a, The MathWorks Inc.).

Given that the purpose of this pilot study is to develop effect sizes for a subsequent R01, we will also derive least-squares means effect sizes of our research strategy on distress, NA, percentage of days of use in 4 intervals [V1-V5; V6-V10; V11-V15; V16-V20]. The number of days that elapsed in each interval will be used as a covariate.

CONFIDENTIAL

This material is the property of the NYU School of Medicine and Langone Medical Center. Do not disclose or use except as authorized in writing by the study sponsor
Interventional Template Version: 11 January 2019

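### K10 recalls four weeks but is analysed over 5-session intervals of 1 to 1.5 weeks, so its per-interval effect sizes cannot describe those intervals

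*Combined protocol and SAP*

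**What the plan says.** Section 8.2.1 defines the K10 as a global distress measure based on anxiety and depressive symptoms "that a person has experienced in the past 4 week period". No shorter-recall version is mentioned, and no recall period is given for the PANAS.

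Section 10.4.2 lists K10 among the dependent measures at visits 1, 5, 10, 15 and 20, with active/sham as fixed effects, "predicting change from V1 values following each 5 session RS-tDCS interval". To support a later R01 application, it also derives least-squares means effect sizes for distress in four intervals, "V1-V5; V6-V10; V11-V15; V16-V20", with the days elapsed in each interval as a covariate.

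On timing, section 8.1 states: "After sessions 5, 10, and 15 participants will complete self-report questionnaires using REDCap survey function". Section 6.1.4 puts the 20 sessions on weekdays, and section 6.1.6 has them run "over the course of approximately 4-6 weeks".

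The primary distress endpoint in section 4.2.1 is "Change in distress measured by Kessler Psychological Distress Scale (K10) and Positive and Negative Affect Schedule (PANAS) between baseline and treatment-end". Section 10.2 states the hypothesis as a treatment-by-time interaction.

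**The concern.** A score that asks about four weeks is used as if it described one block of five sessions. Early in treatment, much of what the participant is asked to recall happened before the first session. Later, consecutive scores largely recall the same weeks. An early K10 change can then be small because the effect starts late or because the question still covers untreated time, and the data cannot say which.

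This bears on a stated product of the pilot: effect sizes by interval for planning a larger trial. The elapsed-days covariate does not help. It adjusts for how long an interval lasted, not for how much of the recall window lies outside it.

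**Working it through.** **Inputs.** Recall window 28 days (8.2.1). K10 scored at baseline and after sessions 5, 10, 15 and 20 (10.4.2, reading its visit numbers as session numbers, as 8.1 implies). Twenty weekday sessions over 4 to 6 weeks (6.1.4, 6.1.6).

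**Interval against window.** Four intervals in 4 weeks last 28/4 = 7 days each; in 6 weeks, 42/4 = 10.5 days. So 28 − 7 = 21 days (75%) or 28 − 10.5 = 17.5 days (63%) of each window lie before the interval that the score is meant to describe. This holds for all four scores, including the last.

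**Share of the window on treatment.** Share = min(day of session / 28, 1), counting session 1 as day 1.

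- Weekday pace, Monday start: days 5, 12, 19, 26.
- Sessions spread evenly over w weeks: day of session k = 1 + (k − 1)(7w − 1)/19. For 5 weeks: 8.2, 17.1, 26.1, 35. For 6 weeks: 9.6, 20.4, 31.2, 42.

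| Pace | Session 5 | Session 10 | Session 15 | Session 20 | Mean |
|---|---|---|---|---|---|
| Weekdays (4 weeks) | 18% | 43% | 68% | 93% | 55% |
| 5 weeks, even | 29% | 61% | 93% | 100% | 71% |
| 6 weeks, even | 34% | 73% | 100% | 100% | 77% |

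The session 5 score is mostly pre-treatment at every pace. The session 10 score is so only at the weekday pace (57% pre-treatment). A weekday course starting on any day but Monday puts the four sessions on days 7, 14, 21 and 28, which gives 25%, 50%, 75% and 100%.

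**Consequence for an averaged arm effect.** Assume that recall weights all 28 days equally, that the effect is immediate and constant, and that the four change scores count equally. The retained fraction f is then the last column: 55%, 71% or 77%. The session 20 score alone keeps 93% to 100%.

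**Link to the sample size.** The stated total reproduces: design effect 1 + (5 − 1) × 0.8 = 4.2, and 50 × 4.2/5 = 42. Section 10.5 thus counts the repeated scores towards power without allowing for recall. Taking its 80% power at one-sided 0.05 at face value, power for the averaged contrast is Φ((1.645 + 0.842) × f − 1.645), or about 39%, 55% and 60% for the three paces. This is an illustration only, because no effect size or SD is given.

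**A gradual effect.** If the effect instead builds linearly over treatment (also an assumption), the four-score average keeps 35%, 46% or 53% of the effect present at the time of scoring. The session 20 score keeps 46%, 60% or 67% of the effect on the last day. The shortfall at session 20 arises almost entirely because the K10 averages over the treatment weeks; at most 7% of its window is pre-treatment.

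**The case against.** The strongest reply is that the trial's primary comparison hardly depends on the interim K10 scores. Section 4.2.1 contrasts baseline with treatment-end, where the window is 93% to 100% on treatment. Section 8.3.5 allows the closing questionnaires up to 3 days apart from session 20, so a weekday participant assessed 3 days later (26 + 3 = 29 days) has a window wholly on treatment. This stands. A reader might infer that the primary distress result is biased toward no effect; the documents do not support that.

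A reader might also infer that the main test loses a quarter to a half of the effect. That needs an arm effect averaged over visits. Section 10.4.2 can be read that way, because it names only active/sham as fixed effects. Section 10.2 tests an interaction with time, however, and treats time as continuous only if plots suggest a trend, which points to categorical visits by default. Under that test, recall lag changes the shape of the interaction without removing the session 20 difference. The 55% to 77% and the power figures therefore belong to one reading only.

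Section 2.1 says that behavioural change follows only a sustained period of daily treatment, so small early differences are expected under any recall period. That is fair, and it rules out saying that the interval effect sizes will certainly be too small. It does not rescue them, because the K10 cannot separate late onset from lag.

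Overlapping windows are not a modelling fault in themselves; a mixed model can carry the correlation. The difficulty is what each estimate means. Finally, the K10 row of the schedule of events cannot be read reliably in the text available, and 8.1 names no instrument, so interim K10 collection rests on 10.4.2.

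**Conclusion.** The mismatch is real and follows from the plan's own recall period and session timing. As planned, none of the four K10 interval effect sizes describes its interval, and the K10 time course cannot be read as onset of effect. The day counts assume the paces shown. The dilution figures further assume equal recall weighting and a specified course of the effect, neither of which the documents give. The treatment-end endpoint is little affected. Nothing here suggests false-positive inflation. The damage is to the interval estimates meant for the R01 and, if 10.4.2 is read as a single arm effect across visits, to that average. It should be corrected in the SAP before analysis.

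**What to change.** In section 10.4.2:

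- State that the K10 conclusion is the arm difference in change from baseline at treatment-end, from a mixed model with visit as a category and an arm-by-visit interaction. This matches section 4.2.1 and removes the averaged reading. The continuous-time option in section 10.2 should then not apply to the K10 conclusion.
- Keep K10 at sessions 5, 10 and 15 in the model only as supporting data for missing treatment-end values.
- Do not report K10 per-interval effect sizes for the R01.
- Use PANAS-NA for the early time course only if section 8.2.1 states its recall period and that period is no longer than the 5-session interval.

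The cost is SAP wording plus a stated PANAS time frame. No participants or visits are added. The downside is that there will be no interim K10 effect sizes.

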8.2.2 Cannabis Use Assessments

- Timeline Followback Method Assessment (TLFB)¹²⁵: self-report questionnaire to assess cannabis type and route of administration, frequency of use (number of days) and frequency of use during the day.
- Daily Sessions, Frequency, Age of Onset, and Quantity of Cannabis-Use Inventory (DFAQ-CU)¹²⁶: 41-item questionnaire to measure frequency, age of onset, and quantity of cannabis used
- Marijuana Craving Questionnaire-17 (MCQ-17)¹²⁷: 17-item questionnaire to assess marijuana craving.
- Cannabis Withdrawal Scale (CWS)¹²⁸: scale to quantify the intensity of withdrawal symptoms, as well as the amount of distress or impairment in functioning due to each symptom.
- Cannabis Single Panel Test⁵⁴: a single panel cannabinoid urine strip test will be used as secondary confirmation of the TLFB. Participant will be asked to collect a urine sample in a sterile urine sample cap right before the video visit. We will ask the participant to complete the test in real time through a live video connection with the study technician to verify and record the test strip reading. This strip test is made for the detection in human urine of cannabinoids and cannabis derivatives. The test is a qualitative assay (type "NO / YES"), and thus delivers a "negative" or "positive" result (cut-off: 50 ng/ml).
- The Cannabis Use Disorder Identification Test – Revised (CUDIT-R): 8-item screening instrument designed to identify potentially problematic or harmful recent cannabis use.

8.2.3 Cognitive and MS symptoms Assessments (Exploratory)

- Brief International Cognitive Assessment in MS (BICAMS)¹²⁹: this battery includes tests of mental processing speed and memory including the Brief Visuospatial Memory Test (BVMT) and Rey Auditory Verbal Learning Test (RAVLT) and Symbol Modalities Digit Test (SDMT).
- SymptoMScreen¹³⁰: 11-item tool to evaluate the symptom severity in domains commonly affected by MS.
- Cogstate Brief Battery (CBB): The core Cogstate RT tasks involve a deck of cards on a green background screen and the participant answers "yes" or "no" by hitting a keyboard key ("D" or "K") across repeated trials. Each task first includes instructions and practice period before the test begins.

CONFIDENTIAL

8.2.4 Additional Assessments

- Wide Range Achievement Test (WRAT-4)¹³¹: an assessment to measure reading and comprehension skills.
- Patient Determined Disease Steps (PDSS): it is a patient-reported scale of disability in MS.

8.3 Study Schedule

8.3.1 Pre-Screening

- Team member conducts phone pre-screening (including WRAT-4, K10, and MS-PDSS) to determine general eligibility based on inclusion/exclusion criteria. Completing these measures over the phone is a practical option that helps screen out those who are ineligible before shipping study materials and it is suitable for phone use as participants can verbally respond to each scale.

On the K10, those who score in the severe mental disorder range (36-50) will be offered to contact the NYU Langone Psychiatry Associates at [contact], or if outside the NY area the Substance Abuse and Mental Health Services Administration (SAMHSA) hotline at [name].

All data collected for the purposes of the eligibility pre-screening will be destroyed immediately if the potential subject is ineligible or does not sign an informed consent form at their baseline.

8.3.2 Electronic Consent & Telehealth medical screening (Visit 1)

- Remote e-consent through SendSafe (*20 minutes*)
- Telehealth medical screen with the study clinician to review medical history and medication history [non-NYU patients may be asked to provide their medical records (e.g. fax to NYU study location)], and determine eligibility based on inclusion/exclusion criteria. (*1 hour*)
- Eligible participants will be scheduled for a baseline visit. A team member who is not involved in the administration of study procedures will randomize and program a tDCS device and study equipment will be shipped to participant.

8.3.3 Baseline Visit & tDCS Session 1 (Visit 2)

- Train participant to use tDCS device (*20 minutes*)
- Perform tDCS tolerability test (*2 minutes*)
- Perform the Cannabis 1 Panel Drug Test (*5 minutes*)
- Self-report questionnaires and measures (*1 hour*)
- Complete first remotely-supervised tDCS session (*20 minutes*)
[First tDCS session and baseline questionnaires may be divided into two sessions +/- 7 days apart pending participant preference]

8.3.4 Remotely-Supervised tDCS sessions 2-19 (Visits 3-20)

- 20x20 minutes of active or sham tDCS with simultaneous mindfulness meditation (*20 minutes*)
- Self-report questionnaires will be administered through MyCap at sessions 5, 10, and 15 (*25 minutes*)
- AE reporting

8.3.5 tDCS Session 20 &Treatment-end Visit (Visit 21)

- Participants will complete tDCS session 20 (*20 minutes*)
- Repeat questionnaires and measures completed at baseline (*1 hour*)
- Perform the Cannabis 1 Panel Drug Test (*5 minutes*)
- Equipment return

CONFIDENTIAL

This material is the property of the NYU School of Medicine and Langone Medical Center. Do not disclose or use except as authorized in writing by the study sponsor
Interventional Template Version: 11 January 2019

[Last tDCS session and post-treatment questionnaires may be divided into two sessions +/- 3 days apart pending participant preference]

8.3.6 1, 2, and 3-month follow-up (months 2, 3, and 4, +/- 7 days) (Visits 22-24)

- Repeat questionnaires (30 minutes)
- Repeat cognitive measures and Cannabis 1 Panel Drug Test (only at 3-month follow-up) (35 minutes)
- Unblind after completing 3-month follow-up and brief blinding integrity questionnaire

8.4 Concomitant Medications, Treatments, and Procedures

All concomitant prescription medications taken during study participation will be recorded on the case report forms (CRFs). For this protocol, a prescription medication is defined as a medication that can be prescribed only by a properly authorized/licensed clinician. Medications to be reported in the CRF are concomitant prescription medications, over-the-counter medications and non-prescription medications.

8.4.1 Precautionary Medications, Treatments, and Procedures

N/A

8.5 Prohibited Medications, Treatments, and Procedures

Treatment with medical cannabis will not be permitted for the duration of this study.

8.6 Participant Access to Study Agent at Study Closure

N/A

9 Assessment of Safety

9.1 Definition of Adverse Events (AE)

An **adverse event** (AE) is any symptom, sign, illness or experience that develops or worsens in severity during the course of the study. Intercurrent illnesses or injuries should be regarded as adverse events. Abnormal results of diagnostic procedures are considered to be adverse events if the abnormality:

- results in study withdrawal
- is associated with a serious adverse event
- is associated with clinical signs or symptoms
- leads to additional treatment or to further diagnostic tests
- is considered by the investigator to be of clinical significance

9.1.1 Definition of Serious Adverse Events (SAE)

Serious Adverse Event

Adverse events are classified as serious or non-serious. A **serious adverse event** is any AE that is:

- fatal
- life-threatening
- requires or prolongs hospital stay
- results in persistent or significant disability or incapacity
- a congenital anomaly or birth defect
- an important medical event

Important medical events are those that may not be immediately life threatening, but are clearly of major clinical significance. They may jeopardize the subject, and may require intervention to prevent one of the

CONFIDENTIAL

This material is the property of the NYU School of Medicine and Langone Medical Center. Do not disclose or use except as authorized in writing by the study sponsor
Interventional Template Version: 11 January 2019

other serious outcomes noted above. For example, drug overdose or abuse, a seizure that did not result in in-patient hospitalization, or intensive treatment of bronchospasm in an emergency department would typically be considered serious.

All adverse events that do not meet any of the criteria for serious should be regarded as ***non-serious adverse events***.

9.1.2 Definition of Unanticipated Problems (UP)

Unanticipated Problems Involving Risk to Subjects or Others

Any incident, experience, or outcome that meets all of the following criteria:

- Unexpected in nature, severity, or frequency (i.e. not described in study-related documents such as the IRB-approved protocol or consent form)
- Related or possibly related to participation in the research (i.e. possibly related means there is a reasonable possibility that the incident experience, or outcome may have been caused by the procedures involved in the research)
- Suggests that the research places subjects or others at greater risk of harm (including physical, psychological, economic, or social harm).

This definition could include an unanticipated adverse device effect, any serious adverse effect on health or safety or any life-threatening problem or death caused by, or associated with, a device, if that effect, problem, or death was not previously identified in nature, severity, or degree of incidence in the investigational plan or application (including a supplementary plan or application), or any other unanticipated serious problem associated with a device that relates to the rights, safety, or welfare of subjects (21 CFR 812.3(s)).

